(a) If for some reason the patient is ordered to stop all oral intakes earlier than the day prior to BC surgery/pre-NAST biopsy, the Pre-surgery visit should be scheduled on the day patient is ordered to stop oral intake; (b) In case the BC surgery/pre-NAST biopsy is planned for a Monday or the day following a holiday; in such cases the Pre-surgery visit should be done on a working day as close as possible to the BC surgery/pre-NAST biopsy (e.g. on a Friday if surgery is scheduled on Monday); or (c) In case that performing Pre-surgery visit on the same day of BC surgery/pre-NAST biopsy is required by site due to logistical reasons or patient's/physician's convenience. Refer to section 6.4.3 for further guidance about the Pre-surgery visit planning and procedures.

4: End of Study visit must be scheduled 30 days (+/- 3 days) after the last intake of darolutamide, even for patients who did not complete the minimum 14 days of protocol treatment. The EoS will be the last study visit for patients. However, for patients experiencing protocol treatment-related AEs/SAEs that are ongoing at the time of the EoS visit, monitoring of these events will continue as clinically indicated until (a) the events have resolved or (b) the events have reached a status which, in the Investigator's opinion, is unlikely to resolve due to the nature of the condition and/or the patient's underlying disease. Frequency of visits will be according to Investigator's judgment.

5: There is no window to obtain the signed and dated PICF. Study-specific screening assessments not considered standard practice by the institution must start only once the PICF has been obtained. Registration takes place as soon as the patient signs the PICF. After screening procedures and if patient meets all eligibility criteria, enrollment will be done according to the process described in section 6.1.2.

6: Complete physical examination will include a complete assessment of body systems (i.e., general appearance, head, eyes, ears, nose, mouth, skin, heart, lungs, lymph nodes, gastrointestinal, genitourinary, skeletal, and neurologic). A complete examination of the breast and regional lymph nodes will also be done.

7: Weight, height and blood pressure must be assessed and collected during screening. Afterwards they will be assessed (as well as other vital signs) according to the SoC.

8: Within 7 days of enrollment, only in WoCBP.

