7. SAFETY MONITORING

7.1 Definitions

7.1.1 Period of Observation

At each visit and any contact during the study and follow-up period, the Investigator or designee will inquire about the occurrence of AEs (and corresponding medications administered) and will document them in the eCRF.

For the purposes of this study, the period of observation for SAEs and AEs extends from the time the patient signs the PICF until the EOS, except for patients that are experiencing AEs or SAEs related to darolutamide ongoing at the time of EoS visit. In such cases, these events will be monitored beyond the EoS visit as clinically indicated until (a) the events have resolved or (b) the events have reached a status which, in the Investigator's opinion, is unlikely to resolve due to the nature of the condition and/or the patient's underlying disease.

The Investigator or designee will report the AEs/SAEs in the eCRF (and, if applicable, to TRIO Safety Department) when required as per the table below:

Table 3: Reporting Period of AEs/SAEs

Study period	AEs (non-serious)	SAEs
From PICF to 1 st intake	Only if related to study participation	All (regardless of relationship)
From 1 st intake until EoS visit	All (regardless of relationship)	All (regardless of relationship)
After the EoS visit	Only if related to protocol treatment	Only if related to protocol treatment

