7.4 Management of Specific Cases

7.4.1 Medication Errors

In the event of a medication error, the patient should be observed closely for signs of toxicity. Medication errors include the accidental or intentional use of darolutamide in a daily dose greater than the protocol-specified daily dose. Appropriate supportive treatment should be provided if clinically indicated. In case of toxicity derived from the medication error, dose modification recommendations from section 5.4.2 should be followed.

The highest darolutamide dose administered in clinical trials is 1,800 mg daily, with no maximum tolerated dose achieved and no dose-limiting toxicity experienced by patients.

If an AE is associated with (“results from”) a medication error, the corresponding AE should be reported as SAE, even if no other seriousness criteria are met.

In cases of a medication error without any associated AE, the medication error should be reported as a non-serious AE, using terminology like “accidental or intentional overdose without adverse effect”, “medication error without adverse effect” or similar.

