3.5.2. Adverse Events (AEs)

AE information will be collected from the time the patient signs the informed consent and continues throughout the trial until EoS. After EoS, AE/SAE information will be collected only if related to the study treatment.

The reported AE term will be coded using the current version of the MedDRA. The severity of AE will be presented as reported by the Investigator based on National Cancer Institute (NCI) Common Terminology Criteria for Adverse Events (CTCAE) grades version 4.03.

Treatment-Emergent Adverse Events (TEAEs) is defined as AEs that start on or after the first dose of investigational treatment or AEs that start before the first dose of treatment but worsened after investigational treatment is initiated.

Incidence of TEAE will be tabulated by SOC, PT for:

- All TEAEs
- TEAEs by relationship to investigational treatment and maximum severity grade
- TEAEs with action taken dose reduced/drug interrupted
- TEAEs with action taken drug withdrawn
- Serious Adverse Events (SAE) (not Serious TEAEs)
- AEs leading to deaths (not Fatal TEAEs) – An AE is considered as leading to death if it reported as Grade 5.

In the event a patient experiences repeat episodes of the same AE according to PT, the event with the highest severity grade will be used for purposes of incidence tabulations.

Detailed listings for all AEs will be provided, including listing with AEs per cohort. A flag will be used to identify which AE is considered as treatment emergent.

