4.1. Planned Tables

| Title | Population | Description |
|---------------------|------------|---|
| Patient Disposition | ITT | Tabulates the disposition of all patients by EBC Subtype, including the number of patients in each population set as well as the number of patients discontinued from investigational treatment, and the number of patients discontinued from trial. The reason for drug discontinuation and trial discontinuation will also be summarized. |
| Protocol Deviations | ITT | Tabulate the number of patients who reported protocol deviations by deviation category for each |

| Title | Population | Description |
|---------------------------------|---------------|---|
| | | EBC Subtype. |
| Eligibility Deviations | ITT | Tabulates the number of patients who violates inclusion/exclusion criteria by criterion for each EBC Subtype. |
| Patient Demographics | ITT Safety | Tabulates summary statistics of the demographics (age, race, ethnicity, menopausal status, weight, height and ECOG status at baseline). |
| Disease Characteristics | ITT | Tabulates summary statistics for time from initial diagnosis to enrollment, primary tumor location, staging at initial diagnosis, histopathological type at initial diagnosis, histopathological grade at initial diagnosis, hormonal receptor status, and HER2 status. |
| Medical History | ITT | Summarizes medical history by SOC and PT for each EBC Subtype. |
| Study Drug Exposure | Safety | Summarizes the duration of treatment, cumulative dose, and RDI by EBC Subtype. The number of dose modifications will also be summarized. |
| Compliance | Safety | Compliance assessment will be summarized. |
| TEAEs Overview | Safety | Tabulates the number of patients with TEAEs, Related TEAEs, Grade 3 / 4 TEAEs, TEAEs with action taken as dose reduced or drug interrupted, AEs leading to drug withdrawn, SAE, Fatal AE. |
| TEAEs | Safety | Summary of number of patients and events by SOC and PT for each EBC Subtype. |
| TEAEs per Maximum Grade | Safety | Summary by SOC and PT of number of patients and events for each EBC Subtype. |
| Related TEAEs | Safety | Summary by SOC and PT of number of patients and events for each EBC Subtype. |
| Related TEAEs per Maximum Grade | Safety | Summary by SOC and PT of number of patients and events for each EBC Subtype. |
| Grade 3 / 4 TEAEs | Safety | Summary by SOC and PT of number of patients and events for each EBC Subtype. |

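### The SAE table and the SAE row of the TEAEs Overview can count SAEs that began before any darolutamide, and no planned table gives serious treatment-emergent events

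*SAP*

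**What the plan says.** SAP 2.2.2 sets the secondary objective as safety and tolerability after short exposure to darolutamide. SAP 3.5.2 opens its list of AE tables with "Incidence of TEAE will be tabulated by SOC, PT for". Two items in that list then depart from the lead-in: "Serious Adverse Events (SAE) (not Serious TEAEs" and "AEs leading to deaths (not Fatal TEAEs". For the second, the SAP adds that "An AE is considered as leading to death if it reported as Grade 5". It gives no reason for the different basis.

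In SAP 4.1, the table titled TEAEs Overview ends with the entries "AEs leading to drug withdrawn, SAE, Fatal AE". SAE and AEs Leading to Death tables by SOC and PT follow. No table of serious TEAEs is listed. All these tables use the Safety population, which SAP 3.1.2 limits to patients who took at least one tablet.

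On collection, Protocol 7.1.1, Table 3 has SAEs between consent and first intake reported as "All (regardless of relationship". Non-serious AEs in that period are reported only if linked to taking part in the study. On the date of consent, footnote 5 of Protocol Table 2 says "There is no window to obtain the signed and dated PICF".

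Protocol 7.4.1 adds a rule for an AE that results from a medication error: "the corresponding AE should be reported as SAE, even if no other seriousness criteria are met".

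**The concern.** Someone reading an SAE row in a table titled TEAEs Overview, or an SAE item under a lead-in about TEAE incidence, will take it as treatment-emergent. It is not. Before the first tablet, SAE collection is complete while non-serious collection is restricted, so serious events are the category in which pre-drug events are most fully captured. Protocol 3.1 prefers consent before the diagnostic biopsy when the diagnosis is still unconfirmed. An unplanned admission after that biopsy would then fall inside the SAE window although no drug had been taken.

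At stake is the count of serious events for an objective about exposure. With cohorts this small, one event of the wrong kind visibly changes a cohort's percentage. The medication-error rule raises a different problem. It can place an event that meets none of the Protocol 7.1.3 criteria in the SAE count, so the row is not purely a count of events serious by those criteria.

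**Working it through.** The plan states no SAE rate for this point, so there is no figure to reproduce. The check is one of definitions, followed by simple proportions.

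**1. Can a pre-dose SAE enter the table?** Three conditions are needed.
- The event is collected: yes, from consent (Protocol Table 3).
- The patient is in the population: yes, if she later takes one tablet (SAP 3.1.2).
- No filter removes it: the SAP expressly declines the treatment-emergent filter for SAEs (SAP 3.5.2).

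The TEAE definition also covers an event that starts before first dose and worsens after it. The events at issue are therefore only SAEs that start before first dose and do not worsen afterwards.

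**2. Can a pre-dose fatal event enter?** A Safety-population patient was alive at first dose, so any Grade 5 event reached Grade 5 on or after that dose. It either started then or later, or started earlier and worsened to Grade 5. Both meet the TEAE definition. In this population, fatal AEs and fatal TEAEs are the same set, and the number of fatal events before any darolutamide is zero by construction. A patient who died before dosing would be in the ITT population only and would appear in the ITT death listing.

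**3. Size of one event.** SAP 2.3 reports 7 triple-negative, 19 HR+/HER2-negative and 10 HER2-positive patients: 7 + 19 + 10 = 36 enrolled. The size of the Safety population is not given, so I assume all 36 were treated. A patient whose only SAE was before first dose adds 1/n:
- overall: 1/36 = 2.8 points
- triple-negative: 1/7 = 14.3 points
- HR+/HER2-negative: 1/19 = 5.3 points
- HER2-positive: 1/10 = 10.0 points

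**4. Chance that at least one occurs.** The documents give no pre-dose SAE risk. With an assumed independent risk p per treated patient, the chance of at least one among 36 is 1 − (1 − p)^36:
- p = 1%: 30%
- p = 2%: 52%
- p = 5%: 84%

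These figures show sensitivity to the assumption and are not estimates for this trial.

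**5. Medication errors.** The error that Protocol 7.4.1 names is taking more darolutamide than the specified daily dose. AEs that result from it therefore follow exposure, and the rule affects seriousness rather than timing. The AE listing in SAP 4.2 shows seriousness and worst grade but not the criterion that made an event serious, so SAEs that qualify only under 7.4.1 are not identified as such.

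**The case against.** The strongest reply is that this is a stated choice that agrees with the protocol. Protocol 8.4 plans SAE summaries with no treatment-emergent limit, the SAP says openly that it does the same, and the overview row is labelled SAE rather than TEAE. Showing all SAEs is the inclusive option. The information can also be recovered: the SAE and Related SAE listings share the structure of the AE listing, which carries a treatment-emergent flag, and where the SAP drops that flag it says so. With 36 patients, reading a listing is feasible. This stands as far as it goes. It means nothing is hidden and the all-SAE summary should stay. It does not supply a serious-TEAE table or correct a misleading title and lead-in.

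Several stronger readings are tempting but not supported:
- A reader might infer that the fatal table counts deaths before darolutamide. Step 2 of the check rules this out.
- A reader might infer that the SAE rate says nothing about exposure. The flagged listings, and the TEAE basis of the related, Grade 3/4 and discontinuation tables, make that too strong.
- A reader might convert pre-dose days into a share of SAEs by assuming an equal daily hazard. The design argues against that. Surgery or NAST comes after dosing, and Protocol 6.4.5 collects AEs from those treatments too. Protocol 7.1.3.2 excludes hospitalisations planned up to enrollment. Patients with a serious event during screening may become ineligible. All three push the pre-dose share of SAEs below its share of time.
- A reader might want a medication error without adverse effect removed from TEAE incidence. Protocol 7.4.1 classes it as a non-serious AE, so removal would contradict the protocol.

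**Conclusion.** The point holds for SAEs and not for deaths. As planned, an SAE that began before first intake and did not worsen afterwards is counted in the SAE table and in the SAE row of a table titled TEAEs Overview, and no planned table isolates serious TEAEs. Each such patient adds 2.8 points overall and 5.3 to 14.3 points within a cohort. This assumes that she has no other SAE, that all enrolled patients were treated, and that the cohort sizes in SAP 2.3 are the analysis denominators. Those sizes rest on local or central subtype, whereas SAP 3.3 analyses by central subtype. Whether any such event occurred cannot be told from the documents.

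The medication-error rule is a second, smaller matter. It mixes events that may meet no other seriousness criterion into the SAE count, but those events do follow exposure. Overall this is a gap in presentation and labelling that is cheap to close. It does not show that the safety analysis is biased to any known degree.

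**What to change.** In SAP 3.5.2 and 4.1:
- Add a table of serious TEAEs by SOC and PT, and a serious-TEAE row in the overview.
- Keep the all-SAE summary that Protocol 8.4 calls for, labelled *all SAEs from consent*, with SAEs starting before first dose on a separate line.
- Correct the lead-in in 3.5.2 so that it does not describe every item as TEAE incidence, and make the overview row labels match. For fatal AEs only the label changes; no pre-dose deaths line is needed.
- Where the recorded data allow, footnote SAEs that are serious only through Protocol 7.4.1. Protocol 7.2.1 confirms that seriousness is collected in the eCRF, but neither document says that the criterion is, so this item depends on what was captured.

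The first three changes need only SAP and table-shell wording and the treatment-emergent flag that the SAP already plans. The cost is the added table and one or two extra overview lines. Expedited reporting and the classification of AEs are unchanged, and every SAE remains visible.

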3.5.3. Laboratory Values

Lab values will be converted to standard units and categorized according to NCI-CTCAE version 4.03. Laboratory results not corresponding to NCI-CTCAE terms will not be graded.

| | | | | | |
|----------------|---------------------------|-----------|----|-----------------|-------------|
| Originated by: | [name] | Revision: | 03 | Effective Date: | 30 Sep 2019 |
| Doc Number: | TRIO030-DM-0025 | | | | |
| Title: | Statistical Analysis Plan | | | | |

Hematology and serum blood chemistry will be summarized in descriptive statistics by calculating the mean, standard deviation, median and range for the following:

- Baseline value
- Minimum post baseline value
- Maximum post baseline value

Shift tables in laboratory toxicity grades (comparing baseline grade with worst post-baseline grade) will be analyzed using standard shift tables, presenting number and proportion of patients and their maximum grade shift.

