6.4.3 Pre-surgery Visit

As a general rule, the Pre-surgery visit will be performed the day before BC surgery or the day before pre-NAST biopsy if NAST is indicated.* If after the Pre-surgery visit takes place, the BC surgery/pre-NAST biopsy planned for the following day is delayed for any reason, the Investigator should contact the Medical Monitor to discuss about potential continuation of darolutamide after the Pre-surgery visit.

During this visit the following assessments will be done:

- Complete physical examination
- ECOG PS
- Safety laboratory assessments:
 - Hematology: Hemoglobin, WBC, ANC and platelets
 - Blood chemistry: AST, ALT, total bilirubin and creatinine
- AEs
- Concomitant medication

Other pre-surgical assessments should be done according to the standard of care (SoC) at the site.

The only exceptions to scheduling the Pre-surgery visit on the day prior to BC surgery/pre-NAST biopsy will be in the following cases:

- a. If the patient is ordered to stop all oral intakes earlier than the day prior to BC surgery/pre-NAST biopsy. In such case the Pre-surgery visit should be scheduled on the day patient is ordered to stop oral intake and all test/assessments should be done at that point.
- b. In case the BC surgery/pre-NAST biopsy is planned for a Monday or the day following a holiday and the Pre-surgery visit cannot be scheduled the day prior to BC surgery/pre-NAST biopsy. In such case the following will be done:
 - The Pre-surgery visit should be done on a working day as close as possible to the BC surgery/pre-NAST biopsy (e.g. on a Friday if surgery is scheduled on Monday).
 - The patient will be instructed to continue with darolutamide intakes until the day prior to BC surgery/pre-NAST biopsy or when she is instructed to stop all oral intakes, whichever occurs first.

- c. In case that performing Pre-surgery visit on the same day of BC surgery/pre-NAST biopsy is required by site due to logistical reasons or patient's/physician's convenience. In such case, it is acceptable that Pre-surgery visit is performed on the same day that BC surgery/pre-NAST biopsy takes place, but before any of those procedures are performed. The results from the laboratory safety tests must be available and reviewed by the Investigator before the BC surgery takes place.

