6.4.5 End of Study Visit

EoS visit must be scheduled 30 days (+/- 3 days) after the last intake of darolutamide, even for patients who did not complete the minimum 14 days of protocol treatment.

The primary purpose of this visit is to follow-up any AEs/laboratory abnormality ongoing at the time of protocol treatment discontinuation and to assess any new AEs/abnormality that may have occurred since protocol treatment discontinuation. Symptom-directed physical examination, ECOG PS assessment and hematology/blood chemistry should be done at this visit. All AEs will be collected (even if due to neoadjuvant treatment, surgery or adjuvant treatment, regardless of the relationship to darolutamide), as well as relevant concomitant treatment according to rules in section 6.5.4.

EoS will be the last study visit with the exception of patients with protocol treatment-related AEs/SAEs that are ongoing at the time of the EoS visit. In these cases, monitoring of these events will continue as clinically indicated until (a) the events have resolved or (b) the events have reached a status which, in the Investigator's opinion, is unlikely to resolve due to the nature of the condition and/or the patient's underlying disease. Frequency of visits will be according to Investigator's judgment.

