6.5.5 Laboratory Assessments

At screening:

- Hematology: Hemoglobin, WBC, ANC and platelets
- Blood chemistry: AST, ALT, total bilirubin and creatinine
- Serum pregnancy test: within 7 days of enrollment, only in WoCBP

At the Pre-surgery and EoS visits:

- Hematology: Hemoglobin, WBC, ANC and platelets
- Blood chemistry: AST, ALT, total bilirubin and creatinine

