8.4 Safety Evaluation

The assessment of safety will be made on the Safety population and will be based mainly on the frequency of AEs. The latest version of the Medical Dictionary for Regulatory Activities (MedDRA) will be used to code all AEs to a preferred term and system organ class. AEs will be graded using the NCI CTCAE v4.03 or according to the applicable grading if the AE is not specifically listed in NCI CTCAE. Patient's incidence of AEs will be tabulated by system organ class, preferred term and toxicity grade for each BC subtype. AEs leading to death or drug discontinuation, drug related and SAEs will also be summarized.

Detailed listings for all AEs will also be provided.

Laboratory parameters: these will be summarized at baseline, along visits and at the EoS visit by each BC subtype, graded according to the NCI CTCAE v4.03. Tables of shifts in toxicity will also be provided.

Other Safety Data: ECOG will be summarized at baseline, along visits and at the EoS visit by BC subtype. Tables of shifts in toxicity will also be provided when applicable.

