3.5.4. ECOG Performance Status

Tabulation of ECOG Performance Status results will be done for the following:

- Baseline value
- Minimum post baseline value
- Maximum post baseline value

A shift table will be provided as well from baseline status to the worst status of post-baseline time points.

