| TEAEs with Action Taken as Dose | Safety | Summary by SOC and PT of number of patients and events for each EBC Subtype. |

| Title | Population | Description |
|---|------------|--|
| Reduced | | |
| TEAEs with Action Taken as Drug Interrupted | Safety | Summary by SOC and PT of number of patients and events for each EBC Subtype. |
| TEAEs Leading to Treatment Discontinuation | Safety | Summary by SOC and PT of number of patients and events for each EBC Subtype. |
| SAE | Safety | Summary by SOC and PT of number of patients and events for each EBC Subtype. |
| AEs Leading to Death | Safety | Summary by SOC and PT of number of patients and events for each EBC Subtype. |
| Laboratory Values | Safety | Summary of each laboratory parameter at baseline, minimum post baseline value, and maximum post baseline value for each EBC Subtype and the total number of patients. In addition, shift tables will be presented. |
| ECOG Performance Status | Safety | Summary of each laboratory parameter at baseline, minimum post baseline value, and maximum post baseline value for each EBC Subtype and the total number of patients. In addition, shift tables will be presented. |
| Concomitant Medications | Safety | Tabulate the frequency and percentage of patients according to Preferred Name. Summary will be presented separately for prior medications and concomitant medications. |

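### The SAP omits the by-visit laboratory and ECOG summaries specified in protocol 8.4, so its summary tables cannot separate end-of-treatment values from End of Study values

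*SAP*

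**What the plan says.** Protocol 8.4 (Safety Evaluation) says of laboratory parameters that "these will be summarized at baseline, along visits and at the EoS visit by each BC subtype", with CTCAE v4.03 grading. It says the same of performance status: "ECOG will be summarized at baseline, along visits and at the EoS visit by BC subtype". It also promises tables of shifts in toxicity, without naming a visit or period for them.

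SAP 3.5.3 describes hematology and chemistry at three points only: baseline, minimum post-baseline and maximum post-baseline. It adds "Shift tables in laboratory toxicity grades (comparing baseline grade with worst post-baseline grade". SAP 3.5.4 repeats the three points for ECOG and adds: "A shift table will be provided as well from baseline status to the worst status of post-baseline time points". The Laboratory Values row of SAP 4.1 matches: "Summary of each laboratory parameter at baseline, minimum post baseline value, and maximum post baseline value for each EBC Subtype". The ECOG row of 4.1 carries the same text, including the reference to laboratory parameters, which looks like a copying slip.

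No table in SAP 4.1 summarizes laboratory values or ECOG by visit or at EoS. No window is set for post-baseline values, so EoS values count.

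**The concern.** Safety and tolerability of short-term darolutamide is the one objective this SAP analyzes, and there is no control arm. What the safety tables can say therefore depends largely on timing: was the value taken while the patient was on drug, or about a month after she stopped and usually after surgery or a biopsy? The protocol's by-visit layout answers that, and the SAP's layout does not.

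The EoS visit also has its own purpose. Protocol 6.4.5 states that "The primary purpose of this visit is to follow-up any AEs/laboratory abnormality ongoing at the time of protocol treatment discontinuation", and it adds the detection of new abnormalities since then. A table that merges EoS with the earlier value shows neither recovery nor new onset.

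**Working it through.** There is no plan figure to reproduce, since SAP 2.3 states that cohort sizes did not come from a formal calculation. The check is a comparison of texts, the visit schedule and one property of the planned statistics.

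**1. Protocol 8.4 against the SAP**
- Laboratory values: the protocol has baseline, visits and EoS, graded, by subtype. The SAP has baseline, minimum and maximum, with grades used only in the shift to worst.
- ECOG: the protocol has baseline, visits and EoS by subtype. The SAP has baseline, minimum and maximum, and a shift to worst.
- Shift tables: the protocol names no time point. The SAP uses the worst post-baseline value, so there is no conflict here.

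**2. Which values enter the tables**
- Protocol 6.5.5 schedules post-baseline laboratory tests "At the Pre-surgery and EoS visits", which makes 2 draws. Each covers 4 hematology items (hemoglobin, WBC, ANC, platelets) and 4 chemistry items (AST, ALT, total bilirubin, creatinine): 4 + 4 = 8 parameters.
- Pre-surgery: by default the last intake is on the morning of this visit (protocol 5.3.2.1). If the visit falls on the day of the procedure, the last intake is normally the day before, and protocol 6.4.3 still places the tests first: "The results from the laboratory safety tests must be available and reviewed by the Investigator before the BC surgery takes place".
- EoS: 30 ± 3 days after last intake (protocol 6.4.5), so 27 to 33 days, and normally after surgery or the pre-NAST biopsy.

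**3. How far EoS is from drug exposure**

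Half-lives elapsed = 24 × days ÷ half-life, with a mean half-life of 11.5 to 16.1 h (protocol 1.2).
- Shortest gap, longest half-life: 24 × 27 ÷ 16.1 = 648 ÷ 16.1 = 40.2
- Longest gap, shortest half-life: 24 × 33 ÷ 11.5 = 792 ÷ 11.5 = 68.9

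On these figures, EoS is effectively a drug-free measurement.

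**4. What the planned statistics can distinguish**

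Let a be the Pre-surgery value and b the EoS value for one patient, with both present and no unscheduled tests. Then min(a, b) = min(b, a), max(a, b) = max(b, a), and the worst grade is likewise unchanged by exchange. For example, the pairs 13 then 11 and 11 then 13 both give minimum 11 and maximum 13. The mean, SD, median and range of the minimum and of the maximum, and the worst-grade shift, are therefore identical if the two visits are exchanged in any set of patients. If the shift table shows x patients, the on-drug count can be anything from the number shifted at both draws, which is not tabulated, up to x.

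**5. ECOG**

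There are normally 2 scheduled post-baseline assessments. A third arises only when treatment exceeds 21 days and the Pre-surgery visit is not within Day 21 ± 3. The v5.0 (Germany) synopsis expects no treatment-period visit. Minimum, maximum and worst are unchanged by any reordering of 3 values as well.

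**6. Cohort sizes**

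SAP 2.3 gives 7 + 19 + 10 = 36 enrolled. These counts are by local or central assessment, whereas SAP 3.3 analyzes by central subtype, so table rows may differ slightly.

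**The case against.** The strongest reply is that little is lost. SAP 4.2 lists every laboratory value and every ECOG assessment, and about 36 patients can be read by eye. Laboratory changes judged clinically relevant, or leading to dose delay or reduction, are recorded as adverse events (protocol 7.1.2) with dates, grade and relationship (protocol 7.2.1), and so reach the adverse event tables. Mock shells were approved with the SAP but not supplied, and may contain by-visit layouts. For protocol v5.0 (Germany) only the synopsis is available.

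This limits the point to summary tables, and mainly to changes not judged clinically relevant. It does not remove the point: a listing is not a summary by subtype, and the SAP text and table list should match the protocol whatever the shells contain.

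Four stronger readings are tempting, and the documents do not support them.
- *The worst-value shift table breaches protocol 8.4.* It does not, because 8.4 sets no time point for shifts.
- *Worst-value tables can only overstate on-drug toxicity.* SAP 3.2.5 uses observed data, so a patient with an EoS draw but no Pre-surgery draw enters the denominator. With hypothetical counts of 5 shifted among 26 Pre-surgery draws and 10 further patients with only an unshifted EoS draw, the on-drug figure is 5/26 = 19.2% but the table shows 5/36 = 13.9%.
- *Pre-surgery always means on drug.* That is only the default. Protocol 5.4.2 withdraws some patients who then go to the procedure, and 8.5 foresees stopping more than 3 days before it.
- *The adverse event tables must also be split by period.* No passage requires this. Protocol 6.4.5 collects events up to EoS whatever their cause, and the related-event and action-taken tables already separate part of them.

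**Conclusion.** The SAP departs from protocol 8.4 by planning no by-visit or EoS summary of laboratory parameters or ECOG, and the supplied text does not explain why. In this schedule the replacement statistics merge a value normally taken at the end of dosing with one taken 27 to 33 days after it. As a result, 8 laboratory parameters and ECOG cannot be read as on-drug change, later change or recovery from the planned summaries.

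The exchange argument assumes that both values are present and that there are no unscheduled tests. The size of any resulting distortion cannot be stated, because the documents give no rates of abnormality at either visit. The departure should be corrected; it affects descriptive safety reporting only, and no inferential result depends on it. Confidence is high for the SAP text and lower for the final layouts, because the mock shells were not available.

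**What to change.** Keep all planned tables. In SAP 3.5.3, 3.5.4 and the Laboratory and ECOG rows of 4.1, restore summaries by subtype at baseline, the treatment-period visit if held (ECOG; no laboratory draw is scheduled then), Pre-surgery and EoS. For laboratory values include CTCAE grade by visit. Footnote patients who stopped drug before the Pre-surgery visit; the date of last dose is already derived in SAP 3.2.3. Correct the ECOG row of 4.1 so that it no longer refers to laboratory parameters. If the mock shells already hold these tables, only the SAP wording needs to change.

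A shift table shown separately for Pre-surgery and for EoS would be a useful low-cost option, but 8.4 does not require it.

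The cost is a few more tables built from the visit label. They are already specified in the protocol, so adding them is not post hoc. The downside is sparse rows in the smallest cohort (about 7 patients), which should be read as descriptive only.
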